7.12.8 Pregnancy

Any pregnancy occurring from date of the informed consent signature until trial completion -must be recorded in the eCRF and reported to PharmaLex as soon as it becomes known to the investigator and not later than within 24 hours of his/her knowledge of the occurrence of the pregnancy (see Section 7.12.10).

The investigator must actively follow-up, document, and report to PharmaLex the progress of the pregnancy until outcome is reached.

7.12.9 Serious adverse event

An SAE is any untoward medical occurrence that at any dose:

- Results in death
- Is life-threatening

- Requires in-patient hospitalisation or prolongation of existing hospitalisation
- Results in persistent or significant disability/incapacity
- Is a congenital anomaly/birth defect
- Other serious or important medical event

Any medical important events that may not result in death, be life-threatening, or require hospitalisation may be considered an SAE when, based on appropriate medical judgment, they may jeopardise the subject or the subject may require medical or surgical intervention to prevent one of the outcomes listed in the above definitions.

The death of a subject enrolled in a trial is per se not an event, but an outcome. Any event resulting in a fatal outcome must be fully documented and reported, regardless of the causality relationship to the IMP.

Any pre-planned hospitalisations that are known at the time of signing the informed consent form will not be recorded as SAEs, however they will be recorded as AEs only.

Any SAE, whether or not deemed IMP-related or expected, must be reported immediately to PharmaLex as soon as it becomes known to the investigator and not later than within 24 hours of his/her knowledge of the occurrence of an SAE (see Section 7.12.10). The investigator will document such events in the best possible detail on the SAE Report Form.

A suspected unexpected serious adverse reaction (SUSAR) is an SAE that is both unexpected (not listed in the Reference Safety Information (RSI) section of the IB, and for which there is evidence to suggest a causal relationship between the drug and the SAE. The Institutional Review Board (IRB)/Independent Ethics Committee (IEC) will be informed of SUSARs according to local requirements. All investigators participating in the trial will also be notified of SUSARs.

Investigator instructions for reporting SAEs are provided in Section 7.12.10.

SAEs occurring after a subject has completed the trial and deemed IMP-related by the investigator should be reported to the sponsor if the investigator becomes aware of them.

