7.12 Adverse events

7.12.1 Adverse events assessments

The investigator or designee is responsible for obtaining, assessing, and documenting all AEs during the trial.

An AE is any untoward medical occurrence in a patient or clinical investigation subject administered an investigational or non-investigational medicinal product and which does not necessarily have to have a causal relationship with this treatment. An AE can therefore be any unfavourable and unintended sign (including an abnormal laboratory finding, for example), symptom, or disease temporally associated with the use of a medicinal product, whether or not considered related to the medicinal product.

All AEs will be documented in the eCRF, including a description of each AE, AE relationship to IMP administration, start and stop dates, seriousness, severity, action taken and outcome.

Any AE that meets the serious criteria must be reported as an SAE to PharmaLex (PLX) within 24 hours of first awareness.

Contact information:

Company: PharmaLex A/S, [name]

E-mail: [contact]

Throughout the trial, the occurrence of AEs should be monitored by nondirective questioning of the subject at each visit. Information on AEs can also be obtained from signs and symptoms detected during examinations, observations made by the trial site personnel, or spontaneous reports from subjects. Pre-existing conditions that worsen during the trial should also be recorded as AEs. This will also include worsening of the disease as judged by the investigator.

AEs requiring therapy must be treated in accordance with recognised standards of medical care to protect the health and well-being of the subject. Treatment due to an AE will be recorded in the subject's records and on the appropriate eCRF.

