7.12.2 Reporting of adverse events

Adverse event information will be collected from individual trial subjects from signature of the informed consent form until the last trial visit.

If the event is reported as an SAE, the timelines for SAE reporting apply (see Section 7.12.10). If the event is reported as non-serious AE, it should be reported on the appropriate eCRF page.

All SAEs and related non-serious AEs must be followed by the investigator until they are resolved or until judged by the investigator to be stable/needing no further follow-up. All

relevant follow-up information will be reported in the eCRF (and to PharmaLex if it qualifies as an SAE, see Section 7.12.1).

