7.12.3 Severity of adverse events

The investigator is to classify the severity (intensity) of an AE according to the following definitions:

- Mild The subject was aware of the signs and symptoms, but the signs and symptoms were easily tolerated and does not interfere with daily activity.
- Moderate The signs and symptoms were sufficient to restrict, but did not prevent, usual daily activity for the subject. The subject is still able to function.
- Severe The subject was unable to perform usual daily activities.

The maximum severity recorded during the course of an AE (mild, moderate, or severe) will be considered the final severity.

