8.7.1 Adverse events

Adverse events will be coded using Medical Dictionary for Regulatory Activities (MedDRA) terminology. Treatment-emergent adverse events (TEAEs), related TEAEs, non-serious TEAEs, serious TEAEs, related serious TEAEs, TEAEs leading to treatment discontinuation and Deaths

will be summarised by the overall incidence of at least one event, incidence by body system, and incidence by body system and preferred term. Each subject will contribute only once (e.g., the first occurrence) to each of the rates, regardless of the number of occurrences (events) the subject experiences. The number of occurrences will also be displayed.

Treatment-emergent AEs will be summarised by severity (mild, moderate, or severe), and by relationship to trial product (not related, unlikely, possibly, or probably). In summaries of severity and relationship, subjects who report more than one event that are mapped to the same preferred term will be counted only once under the strongest severity and relationship, accordingly. An AE is treatment-emergent if its date of onset is on or after the day of start of trial medication. An AE is related if relationship to trial product is not assessed as unrelated.

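### Hospital stays already planned at consent must be recorded as adverse events, against the protocol's own AE definition, and those starting on treatment enter the TEAE tables

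*Protocol*

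**What the plan says.** **Planned stays.** Protocol 7.12.9 states that hospital stays planned and known when consent is signed "will not be recorded as SAEs, however they will be recorded as AEs only". It makes no exception.

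**What an AE is.** Protocol 7.12.1: "An AE is any untoward medical occurrence in a patient or clinical investigation subject administered an investigational or non-investigational medicinal product". The same section has pre-existing conditions recorded as AEs when they worsen during the trial.

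**When AEs are collected.** Protocol 7.12.2: "from signature of the informed consent form until the last trial visit". This includes screening, which the visit schedule (protocol 7.1, Table 3) places on days -28 to -1.

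**When an AE is treatment-emergent.** Protocol 8.7.1 and SAP 5.6.4 decide this by the timing of onset relative to first application. Neither carves out planned procedures.

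**How severity is graded.** Under protocol 7.12.3 the investigator grades each event. Mild and moderate are worded in terms of signs and symptoms. Severe is worded only by function: "The subject was unable to perform usual daily activities".

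**How it is reported.** Protocol 8.7.1: "Treatment-emergent AEs will be summarised by severity (mild, moderate, or severe), and by relationship to trial product". SAP 5.6.4 repeats this and also tabulates non-serious TEAEs. SAP 5.6 limits the safety analysis to descriptive statistics.

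**The concern.** A site that follows 7.12.9 to the letter must enter an AE for an admission that was arranged before the subject joined the trial, even if nothing untoward has happened. No later step removes the entry. If the stay begins on or after first application, it counts towards overall TEAE incidence, non-serious TEAE incidence, and the summaries by severity and relationship.

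The absolute TEAE rates matter because this is the first use of the cream in humans (protocol 2.3). The population makes planned admissions plausible: protocol 2.3 expects many middle-aged to elderly subjects with chronic comorbidities, and protocol 6.6.1 sets a minimum of 40% on dialysis. Events that are not adverse would then be mixed into the safety profile.

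**Working it through.** The documents give no figure to reproduce. The check is mainly one of text, with an illustration of size on assumed inputs.

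**Step 1: is a planned stay an AE?** Section 7.12.1 requires an untoward occurrence, and an admission booked before consent is not one in itself. Recording pre-existing conditions when they worsen points the same way, since an unchanged condition with a booked stay has not worsened.

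**Step 2: can it be an AE but not an SAE?** Section 7.12.9 makes an untoward occurrence serious if it requires in-patient hospitalisation. A stay untoward enough to be an AE would meet that criterion. A stay that is not untoward is neither an AE nor an SAE. The category that 7.12.9 creates fits neither definition. The same section treats death as an outcome and not an event, yet makes a hospital stay with no underlying event an AE.

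**Step 3: which stays become TEAEs?** Only those starting on or after first application. Stays in screening are AEs but not treatment-emergent. If planned stays were spread evenly from consent to Week 12 (assumption), the on-treatment share would be 84/(84 + 28) = 75% with a full 28-day screening period, or 84/(84 + 10) = 89% with an assumed 10-day one.

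**Step 4: illustrated size.** Let b be the true incidence, q the share of subjects with a planned stay on treatment, and s the share of those stays graded severe. Assume independence and the same q in both arms.

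- Reported TEAE incidence = 1 − (1 − b)(1 − q)
- Reported severe TEAE incidence = 1 − (1 − b)(1 − q·s)

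The allocation of 108 subjects at 2:1 gives 72 cream and 36 vehicle. The values of q, b and s are all assumptions.

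| q | Subjects affected, cream / vehicle | TEAE, b = 30% | Severe, b = 5%, s = 0 | Severe, b = 5%, s = 0.5 | Severe, b = 5%, s = 1 |
|---|---|---|---|---|---|
| 2% | 1.4 / 0.7 | 31.4% | 5% | 6.0% | 6.9% |
| 5% | 3.6 / 1.8 | 33.5% | 5% | 7.4% | 9.8% |
| 10% | 7.2 / 3.6 | 37.0% | 5% | 9.8% | 14.5% |

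For example, 1 − 0.70 × 0.98 = 31.4% and 1 − 0.95 × 0.90 = 14.5%.

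Protocol 8.7.1 counts each subject once per rate, so a subject who already has a TEAE adds nothing to overall incidence. At b = 30%, each 1% of subjects affected adds 108 × 0.01 × 0.70 = 0.76 subjects.

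**Step 5: effect on the comparison.** With true incidences b₁ and b₂, the reported difference is

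[1 − (1 − b₁)(1 − q)] − [1 − (1 − b₂)(1 − q)] = (1 − q)(b₁ − b₂).

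A true difference of 10 points becomes 9.8 points at q = 2% and 9.0 points at q = 10%. Ratios move more. If q = 5% and every stay is graded severe, severe rates of 10% and 5% (ratio 2.0) become 1 − 0.90 × 0.95 = 14.5% and 1 − 0.95 × 0.95 = 9.75% (ratio 1.5).

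**The case against.** The strongest defence is that recording planned stays as non-serious AEs is an explicit, over-inclusive choice suited to a first human trial, with little consequence. Much of that stands:

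- A stay arranged before treatment fits the not-related category in protocol 7.12.4, so it should stay out of the related-TEAE table. By rule it is outside the SAE tables.
- TEAEs are listed by subject and tabulated by preferred term, so a reader can find such entries.
- Randomisation and blinding give no reason to expect a difference between arms. Safety is descriptive, so no test or decision rule is affected.
- Several criteria make foreseeable admissions less likely: scheduled transplant, conditions that would impede trial procedures, and likely start of dialysis (protocol 5.3, criteria 2, 10 and 20). Dialysis subjects must have been established on it for at least 3 months (protocol 5.2, criterion 5).

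The defence does not remove the conflict in steps 1 and 2. Caution could justify recording more events, but not a category that contradicts both definitions.

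Three stronger readings are tempting, and the documents support none of them:

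- **That these stays would mostly be counted as severe.** The functional wording of severe makes this possible for an in-patient. But the investigator grades each event, and nothing says how a planned stay is to be graded. The severe columns above run from no change to 14.5% depending only on the assumed q and s.
- **That routine admissions in general become treatment-emergent.** The rule covers only stays planned and known at consent, and only those starting on or after first application become TEAEs.
- **That a real safety difference would be seriously diluted.** Under the stated assumptions the absolute difference shrinks only by the factor (1 − q).

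**Conclusion.** The concern holds as a conflict of definitions with a small consequence. Protocol 7.12.9 requires AE entries that do not meet 7.12.1, and the timing-only TEAE rule carries those starting on treatment into the TEAE and non-serious TEAE tables. Whether any are graded severe is left to the investigator.

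The effect is a modest, non-directional inflation of absolute TEAE rates in both arms. Its size cannot be derived from the documents: neither gives a rate of planned admissions, an expected TEAE rate or a grading share. The figures in the table are illustrations only. The (1 − q) result rests on independence and on an equal share affected in each arm, which randomisation and blinding make reasonable. This is a minor correction and does not threaten the trial's conclusions.

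**What to change.** Reword the sentence in protocol 7.12.9 so that an admission planned before consent is recorded as medical history or as a concomitant procedure, and is not in itself an AE or SAE. State that an AE or SAE is recorded only if the underlying condition worsens, a new event occurs, or the stay is prolonged. The last case agrees with the prolongation criterion already in 7.12.9, and the first with the rule on worsening conditions in 7.12.1. Align the eCRF guidance.

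The cost is one sentence and the matching guidance. The downside is that planned stays appear in the medical history or concomitant procedure listings instead of the AE tables, so a reader who wants every hospital stay must look in both places.

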7.12.10 Reporting of serious adverse events and pregnancies

7.12.10.1 Contact person(s) and number(s)

SAEs and pregnancies must be reported immediately (i.e., not later than 24 hours after first knowledge). The SAE or pregnancy report should be e-mailed or faxed to PharmaLex using the following e-mail or fax-number:

Email: [contact] [contact]

7.12.10.2 Reporting procedures

Serious adverse events

For each SAE, the investigator will complete a Serious Adverse Event Report Form and assess the relationship of each SAE to trial treatment. The completed form(s) should be sent to PharmaLex within 24 hours of first knowledge of the SAE.

Follow-up reports regarding the status of the SAE and the subject's subsequent course should be submitted until the SAE has resolved, is stabilised or needing no further follow-up (in the case of persistent impairment) or the subject dies. The form and acknowledgment of receipt will be retained. Contacts for reporting SAEs, pregnancies and other safety concerns are provided to each site.

7.13 COVID-19 Considerations

COVID-19 control measures in different countries may impact the ability to adhere to some of the trial procedures described in this protocol. Due to challenges that include, but are not limited to, subject preferences, site closures, travel restrictions, and quarantines, some modifications to trial conduct during the COVID-19 pandemic may be necessary to ensure trial continuity. The following are allowable, as necessary, modifications to trial conduct during the COVID-19 pandemic.

- Prior to a trial visit at the site, the subject may be contacted and may be asked to be screened for potential exposure or infection to COVID-19 per local requirements. If the subject is suspected or known to be infected with COVID-19, the on-site visit may either be re-scheduled or a virtual visit may be performed instead, as applicable.
- If a subject cannot attend the regularly scheduled trial visits in person due to COVID-19 necessitating a limit on in-person contact, the investigator may perform safety and efficacy assessments by phone or video to the extent possible. The investigator may use technology platforms that are considered suitable by the site.
- Source documentation and the eCRF should note that the visit was performed virtually (not face-to-face). If certain trial procedures or assessments cannot be completed per the SoA, the reason for the missed assessment must be noted in the source documentation (e.g., COVID-19) and captured in the protocol deviations documentation.

A detailed assessment of COVID-19-related risk and mitigation measures will be documented in the appropriate trial plans, e.g., trial risk management plan.

Subjects who missed significant WI-NRS assessments due to COVID-19 may be replaced if the total number exceeds 10% of subjects enrolled.

8.0 STATISTICAL AND ANALYTICAL PLANS AND DETERMINATION OF SAMPLE SIZE

8.1 General considerations for data analysis

The methodology presented below represents a brief overview of the statistical methods that will be fully detailed in the statistical analysis plan (SAP). The SAP will be finalised before the database is locked. Any changes to the methods described in the final SAP will be described and justified in the clinical trial report. All statistical analyses will be performed using SAS statistical software (Version 9.4 or higher).

Statistical significance will be tested at the two-sided 5% level unless otherwise specified. Superiority is concluded if a p-value of statistical hypothesis testing is below the level and the estimate of treatment difference is in favourable direction for MC2-25 cream.

Categorical variables will be described by summary tables of frequencies (counts and percentages) per treatment group, continuous parameters by displaying arithmetic mean, median, minimum and maximum values, standard deviation, and, where applicable, 1st and 3rd quartiles.

All collected and derived data will be presented in individual subject data listings.

8.2 Sample size and power considerations

Approximately 108 subjects will be randomized in the trial in 2:1 ratio of MC2-25 cream to MC2-25 vehicle, including an assumption of 10% dropouts. For a two-sided test with a 5% level of significance (expected d=1.5 and s=2.46, d/s=0.61) this sample size will provide adequate power (\geq 80%) to compare mean change in WI-NRS from Baseline to Week 12 between MC2-25 cream and MC2-25 vehicle with 72 and 36 subjects (Spencer 2018).

8.3 Analysis populations

The analysis populations are defined as follows:

Screened set (SS): all subjects who sign the informed consent form.

Safety analysis set (SAS): all subjects who are randomized and dispensed the trial medication at Randomisation/Day 0, excluding subjects to whom trial medication is not dispensed or who return all of the trial medication unused. Subjects will be analysed according to the actual treatment.

Full analysis set (FAS): all subjects who are randomized. Subjects will be analysed according to the randomized treatment.

Modified full analysis set (MFAS): all subjects who are randomized and returned for at least one post-baseline scheduled visit with data on WI-NRS. Subjects will be analysed according to the randomized treatment.

Per-protocol set (PPS): a subset of the MFAS subjects who completed the trial with WI-NRS data for Week 12 and are deemed to have no important protocol deviations that could interfere with the objectives of this trial. Important deviations of eligibility criteria and other deviations from the protocol will be assessed. Important deviations from the protocol may lead to exclusion of a subject or data points from the PPS, which could have interfered with the administration of the treatment or the evaluation of treatment effect. All such decisions will be identified and documented before the final trial database is unblinded. Important protocol deviations may include, but are not limited to, medication non-compliance, missing consecutive application days, and intake of prohibited concomitant therapies, which may have an impact on the primary endpoint.

The SAS will be used for all safety analyses. FAS, MFAS, and PPS will be used for efficacy analyses.

8.4 Background and demographic characteristics

For the FAS (and MFAS if it differs from the FAS) and the SAS, summary tables will describe the trial population by treatment group and overall, with regard to demographic and other baseline characteristics. Demographics include age, sex, race, and ethnicity (Section 7.2). Baseline characteristics include medical history, CKD stage and duration, whether subjects are on dialysis or not and time since initiation of dialysis, weekly mean WI-NRS, time since start of CKD-aP, and selected laboratory parameters.

8.5 Trial medication/exposure

Descriptive statistics will be used to summarise trial medication exposure for the SAS. Measures of IMP exposure will include the total duration of treatment, the total weight of trial medication used, the average weight of trial medication used and the total number of applications.

8.6 **Prior and concomitant therapies**

For the SAS, prior and concomitant therapies (as defined in Section 6.7) will be summarized by treatment. Separate summaries will be given for prior therapies, for prior therapies ongoing at baseline, and for concomitant therapies.

8.7 Analysis of safety

On the SAS, safety will be analysed by means of incidences of AEs, abnormalities in laboratory values, vital signs, physical examination and ECG findings. In addition, laboratory values will also be presented as described for continuous variables in Section 8.1.

8.7.1 Adverse events

Adverse events will be coded using Medical Dictionary for Regulatory Activities (MedDRA) terminology. Treatment-emergent adverse events (TEAEs), related TEAEs, non-serious TEAEs, serious TEAEs, related serious TEAEs, TEAEs leading to treatment discontinuation and Deaths

will be summarised by the overall incidence of at least one event, incidence by body system, and incidence by body system and preferred term. Each subject will contribute only once (e.g., the first occurrence) to each of the rates, regardless of the number of occurrences (events) the subject experiences. The number of occurrences will also be displayed.

Treatment-emergent AEs will be summarised by severity (mild, moderate, or severe), and by relationship to trial product (not related, unlikely, possibly, or probably). In summaries of severity and relationship, subjects who report more than one event that are mapped to the same preferred term will be counted only once under the strongest severity and relationship, accordingly. An AE is treatment-emergent if its date of onset is on or after the day of start of trial medication. An AE is related if relationship to trial product is not assessed as unrelated.

